#### 5.4 Storage

Sonazoid vials will be stored in a secure cabinet, with only the study investigators and research personnel having access. The study researchers will be responsible for drug reconstitution and inventory control. Sonazoid is stable for 8 hours after reconstitution. If the agent is suspended and not used within 8 hours it will be discarded.

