direct supervision of a medical doctor. Additionally, resuscitation equipment will be in immediate proximity to the patient during Sonazoid infusion. Three vials (6 ml) of Sonazoid microbubbles (16  $\mu$ l per vial when reconstituted) will be prepared for each subject by resuspending each vial in 2 ml of water for injection, supplied by GEHC, as described in the instructions provided by GEHC (Appendix B). Infusions will be performed as described in Appendix B. All materials and supplies used for the infusion procedure will be identical to those described in GE Healthcare's current Sonazoid IND. Briefly, anintravenous cannula will be placed in a vein in the subject's arm. A 0.9% NaCl solution will be started and used to fill up the connecting tubes before being connected to a 3-way stopcock. The stopcock will then be connected to the extension tubing leading to the cannula. All three vials of suspended Sonazoid will be drawn into a 10 ml syringe, placed in a syringe pump at the same level or below the patient, and connected directly to the stopcock. After the stopcock to the 0.9% NaCl solution has been opened, the saline solution will be infused at a rate of at least 2 ml/min. Then, Sonazoid will be co-infused at the target rate of 0.024  $\mu$ l/kg body weight/minute (suspension infusion rate of 0.18 ml/kg/hour), but the rate may be reduced if necessary to achieve optimal levels of contrast. This infusion rate was selected based on our group's previous experiences with Sonazoid infusion in human subjects in general [Halpern et al. 2002; Landmark et al. 2008] and in SHAPE portal hypertension subjects in particular [Eisenbrey et al. 2013]. This dosing scheme is designed to avoid (or limit) the number of cases that has to be discarded due to insignificant enhancement in the hepatic veins (as in our pilot study; Eisenbrey et al. 2013). The dosage is based off the GEHC provided, study specific resuspension and infusion instructions (Appendix B) and the total Sonazoid dose given over a maximum of 15 minutes (0.36  $\mu$ l/kg) will be well below the maximal tested dose which was still found safe in Phase I clinical trials (2.7  $\mu$ l of microbubbles/kg in PBI 0001 as detailed in the Sonazoid Investigator's Brochure). The duration of contrast agent infusion will range from 5 to 10 minutes.

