## 5. MEDICATIONS

Sonazoid will be provided by GEHC (Oslo, Norway). An FDA Sponsor-Investigator IND application will be submitted to the FDA and studies will not commence until regulatory approval has been obtained from the FDA as well as the IRB committee for TJU and HUP.

Sonazoid is a sterile non-pyrogenic suspension of microspheres of lipid stabilized perfluorobutane (PFB) for contrast-enhancement, with a median diameter between 2.4 and 3.5  $\mu\text{m}$  and less than 0.1 % larger than 7  $\mu\text{m}$ . Sonazoid is formulated as a powder for injection consisting of lyophilized sucrose entrapping hydrogenated egg phosphatidyl serine (HEPS) PFB microspheres under a PFB headspace. Each milliliter of Sonazoid contains roughly 1.2 billion microspheres.

Sonazoid is supplied as a dry powder within 10 ml sealed vials. The headspace of the vials contains PFB. Three vials with 48  $\mu\text{l}$  of Sonazoid microbubbles (6 ml) will be prepared for each subject by resuspending each vial in 2 ml of injection grade water supplied by GEHC, as described in Appendix B. Infusions will be performed as described in the Instructions for Use protocol supplement provided by GEHC (Appendix B). All materials and supplies used for the infusion procedure will be identical to those described in GE Healthcare's current Sonazoid IND. A diagram of this infusion setup is shown below in Figure 1.

**Figure 1:** Setup used for Sonazoid infusion for all patients during SHAPE imaging. This setup is discussed briefly in section 5 and in detail in the attached GEHC provided infusion protocol (Appendix B).

Briefly, a 20-22 gauge cannula will be placed in a vein in the subject's right or left arm. A 0.9%NaCl solution will be started and used to fill up the connecting tubes before being connected to a 3-way stopcock. The stopcock will then be connected to the extension tubing leading to the cannula. All three

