## 6.2 Treatment Administration

Administration of Sonazoid will be performed under direct supervision of a medical doctor. Emergency services (e.g., a crash cart) will be available within the hospital in case of any acute adverse reactions. Additionally, resuscitation equipment will be in immediate proximity to the patient during Sonazoid infusion. Patients will be monitored for AEs post Sonazoid treatment for a minimum of one hour. Trained CPR personnel and resuscitation equipment will be in attendance during this monitoring period. A dose of three vials with 48  $\mu$ l of Sonazoid microbubbles (6 ml total after resuspension) will be prepared for each subject by resuspending each vial in 2 ml of injection grade water supplied by GEHC. Infusions will be performed as described in the GEHC protocol supplement (Appendix B), and shown in Figure 1. All materials and supplies used for the infusion procedure will be identical to those described in GE Healthcare's current Sonazoid IND. Briefly, an IV cannula will be placed in a vein in the subject's right arm. A 0.9%NaCl solution will be started and used to fill up the connecting tubes before being connected to a 3-way stopcock. The stopcock will then be connected to the extension tubing leading to the stopcock the cannula. All three vials of suspended Sonazoid will be drawn into a 10 ml syringe, placed in a syringe pump at the same level or below the patient, and connected directly to the stopcock. After the stopcock has been opened, the NaCl solution will be infused at a rate of at least 2 ml/min, and Sonazoid will be infused at the desired rate of 0.024  $\mu$ l/ kg body weight/ minute (suspension infusion rate of 0.18 ml/kg/hour), but may be reduced if necessary to achieve optimal levels of contrast . This infusion rate was selected based on our group's previous experiences with Sonazoid infusion in human subjects in general [Halpern et al. 2002; Landmark et al. 2008] and in SHAPE portal hypertension subjects in particular [Eisenbrey et al. 2013]. This dosing scheme is designed to avoid (or limit) the number of cases that has to be discarded due to insignificant enhancement in the hepatic veins (as in our pilot study; Eisenbrey et al. 2013). This dosage is based off the GEHC instructions for storage and well below the maximal tested dose which was still found safe in Phase I clinical trials (2.7  $\mu$ l of microbubbles/kg in PBI 0001 as detailed in the Sonazoid Investigator's Brochure).

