## 5 STORAGE OF RECONSTITUTED PRODUCT

If the reconstituted product is not used immediately, leave the vial at rest in an upright position. Store between 15-25°C.

**NOTE** - The infusion procedure must be started **within 1 hour** from reconstitution of the product.

**NOTE** - Always shake the product for 10-15 seconds before withdrawal from the vial.

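### Section 5.4 sets an 8-hour discard point for suspended Sonazoid, but Appendix B, which the protocol adopts, requires infusion to start within 1 hour of reconstitution

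*Combined protocol and SAP*

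**What the plan says.** Section 5.4 (Storage) says that reconstituted Sonazoid is stable for 8 hours and then sets a handling rule: "If the agent is suspended and not used within 8 hours it will be discarded". It also says who applies it: "The study researchers will be responsible for drug reconstitution and inventory control".

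Appendix B, section 5 (Storage of reconstituted product), sets a different limit on the same product: "The infusion procedure must be started within 1 hour from reconstitution of the product".

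The protocol body makes Appendix B part of the procedure in several places:

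- **Preparation.** The synopsis has the vials resuspended "as described in the instructions provided by GEHC (Appendix B"). Section 5 (Medications) repeats this: "resuspending each vial in 2 ml of injection grade water supplied by GEHC, as described in Appendix B".
- **Infusion.** Section 5 says "Infusions will be performed as described in the Instructions for Use protocol supplement provided by GEHC (Appendix B"), and section 6.2 (Treatment Administration) says "Infusions will be performed as described in the GEHC protocol supplement (Appendix B), and shown in Figure 1".

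**The concern.** Both limits run from the moment the powder is suspended, and both apply to the same vials. They differ by a factor of eight, and the protocol does not rank them. A researcher who relies on section 5.4 could reasonably conclude that product reconstituted three hours ago may still be given. A researcher who follows Appendix B would discard it.

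What is at stake is the handling of an investigational injectable at two sites. The body of the protocol is looser than the manufacturer's supplement it adopts. It is also unclear whether an infusion begun at, say, 90 minutes is a protocol deviation, although Appendix A, part E, requires prior written approval for deviations. No consequence for the pressure estimates, the sample size or the planned analyses is claimed.

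**Working it through.** The plan has no figure to reproduce here. The check is a comparison of the two rules, followed by simple arithmetic on timing.

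**Step 1: the two rules by time since reconstitution**

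| Infusion starts | Section 5.4 | Appendix B, section 5 |
|---|---|---|
| Up to 1 hour | allowed | allowed |
| Between 1 and 8 hours | allowed (discard point not reached) | not allowed |
| After 8 hours | discard | not allowed |

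The rules disagree over 8 − 1 = 7 hours, that is, for 7 of the 8 hours that section 5.4 leaves open.

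**Step 2: does either text give way?** The sentence on 8-hour stability can stand beside a 1-hour operating limit. The sentence after it cannot, because it says when suspended product must be thrown away if unused, which is itself an operating rule. On the other side, the Appendix B limit is mandatory in its wording and sits under that appendix's own heading on storage of reconstituted product. No sentence in either place refers to the other.

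**Step 3: could the gap be reached in an examination day?** The documents do not fix when vials are reconstituted. As an illustration only, assume this happens at the start of the examination window, and keep the required post-dose observation ("Patients will be monitored for AEs post Sonazoid treatment for a minimum of one hour") inside that window.

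Inputs:

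- Window: 2 hours after biopsy (section 3.1), or 3 hours of post-recovery observation (synopsis, Trial Procedures)
- Monitoring after Sonazoid: 60 minutes (synopsis; sections 3.1 and 6.2)
- Infusion: 5 to 10 minutes (synopsis), with a maximum of 15 minutes (Appendix B, section 6.2)

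Latest infusion start = window − monitoring − infusion time.

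| Window | 5-min infusion | 10-min infusion | 15-min infusion |
|---|---|---|---|
| 120 min | 120 − 60 − 5 = 55 | 120 − 60 − 10 = 50 | 120 − 60 − 15 = 45 |
| 180 min | 180 − 60 − 5 = 115 | 180 − 60 − 10 = 110 | 180 − 60 − 15 = 105 |

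In the 2-hour window, a 5- to 10-minute infusion starts at the latest at 50 to 55 minutes, which is 5 to 10 minutes inside the 1-hour limit. In the 3-hour window the latest start is 110 to 115 minutes, which is 50 to 55 minutes beyond it. Reconstituting later in the window shortens these intervals one for one. The illustration shows only that the timetable does not rule out a breach. It says nothing about frequency.

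**The case against.** The strongest reply is that the two texts do different jobs. Section 5.4 is a storage section. It never says that an infusion may begin at 8 hours; it states stability and an outer discard point, and permission to use the product until then is only implied. Appendix B governs the specific act of starting the infusion, and because the body says infusions follow Appendix B, the specific and stricter instruction would naturally control. Staff who follow it comply with both.

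The rest of the procedure also works against long holds. Section 5 requires new vials for each subject. Appendix B, section 3, describes a short reconstitution with one minute of shaking per vial, and its section 6.2 has the product drawn up immediately before the infusion. Staff preparing vials are sent to the appendix, where the 1-hour note comes soon after the reconstitution steps. The timing illustration depends on early reconstitution, which nothing in the plan calls for, and shows no breach in the 2-hour window. Finally, the documents do not say that product older than 1 hour is unsafe or degraded.

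Most of this stands, and it is why the point is minor. It makes a breach less likely and leaves harm unshown. It does not remove the conflict. The discard sentence in section 5.4 tells those responsible for reconstitution when to throw product away, and the time it gives is 7 hours later than the adopted supplement allows an infusion to start. The precedence of Appendix B is a sensible inference, but the plan does not state it.

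**Conclusion.** The concern holds as a minor internal inconsistency in drug handling. For infusions started between 1 and 8 hours after reconstitution, a span of 7 hours, section 5.4 and Appendix B, section 5, give opposite answers, and the plan does not settle which applies.

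This conclusion rests on the wording of the two sections and on the adoption of Appendix B in the synopsis and in sections 5 and 6.2. It does not depend on the timing illustration, whose 50 to 55 minutes of possible excess requires both the 3-hour window and reconstitution at its start. How often the gap would be reached is unknown. The documents give no basis for either limit, so they cannot show which one is pharmaceutically correct, only that the plan should state one.

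**What to change.** Replace the discard sentence in section 5.4 with a rule that infusion must start within 1 hour of reconstitution and that product not started by then is discarded. If the manufacturer confirms a different limit in writing, amend section 5.4 and Appendix B, section 5, together so that they carry the same figure.

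This is a one-sentence protocol correction. Its practical cost is an occasional extra set of three vials when an examination is delayed after reconstitution.

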### 6. TRIAL PROCEDURES

#### 6.1 Screening Assessments

Screening assessments will be performed within 4 weeks prior to the administration of Sonazoid. All subjects will receive a written consent form and a verbal explanation of the trial by the investigator and/or the research study coordinator and will be asked to sign the written informed consent. Trial participants will have the presence of inclusion criteria and absence of exclusion criteria verified by providing a comprehensive medical history, which will include screening assessments for their scheduled transjugular liver biopsy. Patients with cardiac shunts will be excluded from the study.

## 6.2 Treatment Administration

Administration of Sonazoid will be performed under direct supervision of a medical doctor. Emergency services (e.g., a crash cart) will be available within the hospital in case of any acute adverse reactions. Additionally, resuscitation equipment will be in immediate proximity to the patient during Sonazoid infusion. Patients will be monitored for AEs post Sonazoid treatment for a minimum of one hour. Trained CPR personnel and resuscitation equipment will be in attendance during this monitoring period. A dose of three vials with 48  $\mu$ l of Sonazoid microbubbles (6 ml total after resuspension) will be prepared for each subject by resuspending each vial in 2 ml of injection grade water supplied by GEHC. Infusions will be performed as described in the GEHC protocol supplement (Appendix B), and shown in Figure 1. All materials and supplies used for the infusion procedure will be identical to those described in GE Healthcare's current Sonazoid IND. Briefly, an IV cannula will be placed in a vein in the subject's right arm. A 0.9%NaCl solution will be started and used to fill up the connecting tubes before being connected to a 3-way stopcock. The stopcock will then be connected to the extension tubing leading to the stopcock the cannula. All three vials of suspended Sonazoid will be drawn into a 10 ml syringe, placed in a syringe pump at the same level or below the patient, and connected directly to the stopcock. After the stopcock has been opened, the NaCl solution will be infused at a rate of at least 2 ml/min, and Sonazoid will be infused at the desired rate of 0.024  $\mu$ l/ kg body weight/ minute (suspension infusion rate of 0.18 ml/kg/hour), but may be reduced if necessary to achieve optimal levels of contrast . This infusion rate was selected based on our group's previous experiences with Sonazoid infusion in human subjects in general [Halpern et al. 2002; Landmark et al. 2008] and in SHAPE portal hypertension subjects in particular [Eisenbrey et al. 2013]. This dosing scheme is designed to avoid (or limit) the number of cases that has to be discarded due to insignificant enhancement in the hepatic veins (as in our pilot study; Eisenbrey et al. 2013). This dosage is based off the GEHC instructions for storage and well below the maximal tested dose which was still found safe in Phase I clinical trials (2.7  $\mu$ l of microbubbles/kg in PBI 0001 as detailed in the Sonazoid Investigator's Brochure).

## 6.3 Trial Assessments

### 6.3.1 Medical History

A full demographic profile, known drug allergies or intolerances, and a review of the subject's medical/surgical history will be recorded. If the subject is a woman of childbearing potential, she will have a urine pregnancy test (the results of which will be made available to the subject prior to study initiation). Emergency services (e.g., a crash cart) will be available within the hospital in case of any acute adverse reactions. Adverse events will be monitored during the entire procedure.

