Trial Design: This is an open-label, non-randomized trial that will be conducted at two clinical sites, Thomas Jefferson University (TJU) and the Hospital of the University of Pennsylvania (HUP). Enrolled patients undergoing trans-jugular liver biopsy with hepatic vein pressure gradient (HVPG) measurements will receive a continuous infusion of Sonazoid® (GE Healthcare, Oslo, Norway) co-infused with 0.9% NaCl solution over a 5-10 minute time period using the setup and infusion rates described in GE Healthcare (GEHC) Protocol Supplement provided in Appendix B. Ultrasound imaging will be performed using a Logiq 9 scanner with a 4C transducer (GE Healthcare, Milwaukee, WI) and the SHAPE algorithm will be used to measure pressure values in the hepatic and portal veins. Data will be stored on a PC and compared to pressure-catheter measurements. Subjects identified in the initial examination as having portal hypertension (by HVPG results) will be monitored by SHAPE for up to 18 months. These subjects typically have surveillance CT or MRI scans every 6 months to screen for liver cancer, and at those times a repeat SHAPE examination will be performed (ideally within 1 month of their clinically indicated imaging follow up appointment). In patients who undergo more frequent screening (generally 3 month intervals), SHAPE exams will be performed at 6 month intervals. Any repeat trans-jugular liver biopsies performed in this population will also trigger a repeat SHAPE study. Results of blood test evaluations (performed every 3 months in this population), medication, concomitant imaging study or procedure (including endoscopies) will be noted (all blood tests and imaging are clinically indicated only and are not required by this protocol). The end point for this part of the study will be any one new complication (e.g., liver cancer) or a marked worsening in any complication, liver

transplantation, death, or the end of this clinical trial (after 3 years). We expect these patients will be monitored three times during the course of this clinical trial. The time to reach the end point will be noted if a new complication or a marked worsening in any complication occurs.

**Trial Population:** This trial will consist of up to 300 adults (21 years of age or older) undergoing trans-jugular liver biopsy with HVPG measurement at TJU or at HUP.

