## 3. TRIAL DESIGN

This is an open-label, non-randomized trial that will be conducted at two clinical sites, Thomas Jefferson

University (TJU) and the Hospital of the University of Pennsylvania (HUP). Enrolled patients undergoing trans-jugular liver biopsy will receive a continuous infusion of Sonazoid® (GE Healthcare, Oslo, Norway) co-infused with 0.9% NaCl solution over a 5-10 minute time period using the setup and infusion rates described in GE Healthcare (GEHC) Protocol Supplement provided in Appendix B. Ultrasound imaging will be performed using a Logiq 9 scanner with a 4C transducer (GE Healthcare, Milwaukee, WI) and the SHAPE algorithm will be used to measure pressure values in the hepatic and portal veins. Data will be stored on a PC and compared to pressure-catheter measurements, which are taken as part of the standard of care for all patients undergoing a trans-jugular biopsy. Subjects identified in the initial examination as having portal hypertension (by HVPG results) will be monitored by SHAPE for up to 18 months. These subjects typically have surveillance CT or MRI scans every 6 months to check for liver cancer and at those times a repeat SHAPE examination will be performed (ideally within 2 weeks). Any repeat transjugular biopsies performed in this population will also trigger a repeat SHAPE study. Results of blood test evaluations (performed every 3 months in this population), medication, concomitant imaging study or procedure (including endoscopies) done as standard of care will be noted. The end point for this part of the study will be any one new complication (e.g., liver cancer) or a marked worsening in any complication, liver transplantation, death, or the end of the clinical trial participation (up to 18 months). On an average, these patients will be monitored three times during the course of this clinical trial.

A full demographic profile, known drug allergies or intolerances, and review of the subject's medical/surgical history will be recorded. If the subject is a woman of childbearing potential, she will have a urine pregnancy test (the results of which will be made available to the subject prior to study initiation).

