### 3.1 Trial Duration

Individual participation in this trial will be limited to ultrasound imaging studies within the two hour period following a trans-jugular liver biopsy (during which their hepatic wedge pressure will be measured

with a pressure catheter as part of the standard of care at TJU and HUP). Patients are monitored for two hours (1 hour post Sonazoid injection). The entire ultrasound imaging protocol will require approximately one hour. Subjects identified in the initial examination as having portal hypertension (by HVPG results) will be monitored by SHAPE for up to 18 months. These subjects typically have surveillance CT or MRI scans every 6 months to check for liver cancer and at those times a repeat SHAPE examination will be performed. Any repeat trans-jugular biopsies performed in this population will also trigger a repeat SHAPE study. Moreover, these patients will have a complete blood test every 3 months and these clinical variables (platelets, albumin, MELD, etc.) as well as any medication will be recorded. Finally, most subjects with portal hypertension will undergo an endoscopy examination every 1 to 2 years [de Franchis 2005; Merkel et al. 2004]. Results of any concomitant imaging study or procedure (including endoscopies) will be noted. The end point for this part of the study will be any one new complication (e.g., liver cancer) or a marked worsening in any complication (e.g., MELD scores), liver transplantation, death, or the end of this clinical trial (after 3 years). On an average, these patients will be monitored three times during the course of this clinical trial. The time to reach the end point will be noted if a new complication or a marked worsening in any complication occurs.

Subject recruitment is expected to last 3 years (April, 2014 – January, 2017). This includes monitoring disease progression and/or treatment response. Analysis and publication of results are expected to take an additional 2 months (January– March, 2017). Volunteer Registry Database forms will be submitted to the National Institute of Health’s Office of Regulatory Compliance and Quality at the completion of the research study.

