#### 4.1 Inclusion Criteria

All subjects accepted for this trial must fulfill all the following criteria:

- Be scheduled for trans-jugular liver biopsy the day of the ultrasound procedure.
- Be at least 21 years of age.
- Be medically stable.
- If a female of child-bearing potential, must have a negative pregnancy test.
- Be conscious and able to comply with study procedures.
- Have read and signed the IRB-approved Informed Consent form for participating in the study.

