### 6.3.2 Ultrasound Imaging

The ultrasound examinations will be performed by a qualified sonographer. Procedures and equipment for this trial will be used in accordance with typical clinical procedures. All trial procedures will be conducted in accordance with Good Clinical Practice. A modified Logiq 9 scanner (GE Healthcare, Milwaukee, WI) with a broad bandwidth curvi-linear array will be used in to obtain RF data (for SHAPE measurements) within the hepatic and portal veins. Both the experimental machine and software will be labeled as an investigational device with a GE provided label prior to beginning any clinical experiments (21 CFR 812.5). Ultrasound imaging will be performed at a transmit frequency of 2.5 MHz and the subharmonic obtained at 1.25 MHz. Using this setup, acoustic pressure amplitudes will all be below 1.21 MPa peak negative pressure, 2.19 MPa peak positive pressure. The SHAPE algorithm will be activated and the acoustic power will be adjusted to produce the maximum change in subharmonic amplitudes (i.e., maximizing the sensitivity of SHAPE). Subharmonic data from the microbubbles (i.e., SHAPE) will be acquired in 5 s segments during the infusion of the Sonazoid suspension. All measurements will be repeated three times.

During the examination, the subharmonic pressure estimates will be displayed on the Logiq 9 scanner, these estimates will be noted and the data will be stored on a PC. Data will be compared to the

transcatheter portal pressure measurements, which comprise the free and wedged hepatic venous pressure (FHVP and WHVP, respectively) and the hepatic vein pressure gradient (HVPG; measured as the difference between the WHVP and FHVP), which are acquired as part of standard of care for all patients undergoing trans-jugular liver biopsy at TJU and HUP.

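### The plan states no repeat pregnancy test before the follow-up Sonazoid infusions at about 6, 12 and 18 months

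*Combined protocol and SAP*

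**What the plan says.** **Pregnancy test.** Section 6.3.1 provides that, if the subject is of childbearing potential, "she will have a urine pregnancy test (the results of which will be made available to the subject prior to study initiation"). The same sentence stands in the Synopsis (Trial Procedures) and in Section 3. Section 4.1 adds the entry condition "If a female of child-bearing potential, must have a negative pregnancy test", without a time window. Section 4.2 excludes pregnant or nursing women.

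**Screening.** Section 6.1 states: "Screening assessments will be performed within 4 weeks prior to the administration of Sonazoid". It then describes consent, followed by verification of the criteria through a medical history, "which will include screening assessments for their scheduled transjugular liver biopsy".

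**Follow-up.** Subjects with portal hypertension by HVPG are monitored by SHAPE for up to 18 months. Section 3 links the repeats to six-monthly surveillance CT or MRI: "at those times a repeat SHAPE examination will be performed". For patients imaged more often than that, the Synopsis says "SHAPE exams will be performed at 6 month intervals".

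**What an examination involves.** Under Section 6.3.2 the subharmonic data "will be acquired in 5 s segments during the infusion of the Sonazoid suspension".

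**The concern.** The protocol treats a pregnancy test as necessary before the first infusion. It gives no reason why later infusions of the same agent, months afterwards, should need less. An exclusion for pregnancy works only if the pregnancy is known, and an early one may be known to neither the patient nor the investigator.

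What is at stake is subject safety in the follow-up part of the trial. The Synopsis notes that Sonazoid is not FDA-approved. The serious adverse event definition includes a birth defect in a subject's offspring. That item belongs to a general definition and is not evidence of fetal harm from this agent, but it does show that the outcome is one the protocol would have to report.

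**Working it through.** The plan gives no figure to reproduce. The check is a reading of the sections side by side, plus simple timing arithmetic.

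**Step 1: when is the test done?** Three places describe it (Synopsis, Section 3, Section 6.3.1), all with the result available before the study starts. In the Synopsis and in 6.3.1 it is listed with the demographic profile, drug allergies and medical history, which are items collected at entry. Section 4.1 requires a negative result but adds no timing.

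**Step 2: does eligibility screening recur?** Section 6.1 is the only description of eligibility verification. The steps under its 4-week window are consent and the work-up for the scheduled biopsy. No follow-up visit is mentioned.

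**Step 3: is there re-exposure?** No sentence says in so many words that Sonazoid is given at the follow-up visits. It follows from the method, because SHAPE reads subharmonic signals from the microbubbles and Section 6.3.2 acquires them during infusion. Section 6.7.1 also counts a subject as complete after at least one infusion, which allows for more than one.

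**Step 4: how many repeats, and how old is the result?**
- Scheduled repeats over full follow-up: 18 months / 6 months = 3, at about months 6, 12 and 18.
- Age of the result = months × 52/12:
  - month 6: 6 × 52/12 = 26 weeks
  - month 12: 12 × 52/12 = 52 weeks
  - month 18: 18 × 52/12 = 78 weeks
- Compared with the 4-week screening window: 26/4 = 6.5, 52/4 = 13 and 78/4 = 19.5 times as long.

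These ages count from the index infusion. A test done up to 4 weeks before it would be older by that amount.

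**Step 5: would anything else detect an unrecognised pregnancy?** Section 6.2 puts a physician in direct supervision of dosing. Section 6.7.1 lets the investigator withdraw a subject when continuing is unsafe, and a new complication ends follow-up. None of these is a test for pregnancy. The follow-up data to be noted are blood tests, medication, imaging and procedures. The Synopsis says the blood tests and imaging are done only when clinically indicated, and no pregnancy test is named.

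**The case against.** The strongest reply is that the wording may already cover repeats. The protocol also uses the word study for a single examination: a repeat biopsy triggers a repeat SHAPE study, and Section 6.7.1 refers to the ultrasound imaging study. On that reading, the test precedes each SHAPE study. Likewise, the 4-week window in Section 6.1 could be taken to apply to every administration. Both readings are possible but strained, since the test is grouped with entry items and the 4-week window with consent and the biopsy work-up. If either reading is what the sponsor intends, one sentence would settle it.

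A second reply is that consent pages and some other pages are not available for review and may carry pregnancy instructions. That is fair, and the point is limited to the visible text. For the same reason, nothing should be inferred from the absence of a contraception rule in Sections 4.1 and 4.2.

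A reader might go further and infer that none of the exclusions is checked again before re-dosing. The documents do not support that:
- Section 4.2 is not worded as applying at entry only. Some of its items are tied to dosing or to the examination, such as recent investigational drugs and surgery within the preceding 24 hours.
- Interval blood tests, medication, imaging and procedures are recorded during follow-up.
- The sonographer locates the portal and hepatic veins at the examination.
- A new complication ends follow-up.

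Nor is it a defect that a surveillance visit cannot meet the biopsy-scheduling criteria, because the follow-up text expressly provides for those visits. An unrecognised pregnancy is different, since none of these steps would reveal it.

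**Conclusion.** The point holds for the pregnancy test alone. On the visible text, a woman of childbearing potential could follow the plan exactly and receive Sonazoid on a result about 26, 52 or 78 weeks old, at up to three scheduled repeats.

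This rests on two readings: that each repeat SHAPE examination includes an infusion, which the method implies, and that the stated timing refers to trial entry, which is the more natural sense. The documents do not give the number of women of childbearing potential with portal hypertension, so neither the number of infusions affected nor the chance of an exposed pregnancy can be estimated. No fetal-risk data are given, so harm is not shown.

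Aim 1, its analysis and the sample size of 300 are unaffected. This is a low-cost safety improvement and does not bear on the validity of the trial.

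**What to change.** Amend Section 6.3.1, and the matching sentences in the Synopsis and Section 3, to say that women of childbearing potential must have a negative urine pregnancy test before each Sonazoid infusion, including every repeat SHAPE examination, and that the result must be known before dosing starts.

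The cost is one urine test per repeat visit for the women concerned. A few repeat examinations may not go ahead, which would slightly reduce the follow-up data for H3 and H4. If the sites already test at each visit, the amendment only documents what they do.
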